7.3 Screening

After enrollment, subject eligibility will be assessed and documented during screening. Eligibility may be assessed by subject interview or through a review of the medical chart against the eligibility criteria. Subjects meeting all eligibility criteria will be considered as screen pass and will continue with the study. Subjects not meeting the eligibility criteria will be considered screen fails and exited from the study.

7.4 Screen Fails

Enrolled subjects who do not meet eligibility criteria will be considered screen fails and exited from the study. Screen fails will be documented on the Screen Fail CRF and will be analyzed for safety endpoints only.

7.5 Study Procedure – Single Clinic Visit

The study requires a single clinic visit by study subjects for up to two ARM procedures. Each subject will undergo a standard ARM procedure using the Solar Catheter in accordance with standard of care, device IFU and the IAPWG standardized testing protocol and London classification for ARM measurement where, at minimum, the following parameters are collected:

- Functional anal canal length, cm
- Anal resting pressure, mmHg
- Anal squeeze pressure, mmHg
- Push pressure, mmHg
- Cough pressure, mmHg

The International Anorectal Physiology Working Group (IAPWG) recommended IAPWG standardized testing protocol and London classification of anorectal disorders provide a standardized format for performing and interpreting ARM. No additional tests or assessments are being requested for the purposes of this data collection beyond what is considered as standard for conducting ARM measurements.

A subset of subjects will undergo a second ARM procedure using the UNITIP catheter in accordance with standard of care, device IFU and the IAPWG standardized testing protocol and London classification for ARM measurement.

Adverse events (AEs) and device malfunctions will be assessed and reported according to Section 12.3

7.6 Study Exit

Subjects' participation in the study consists of one clinic visit. Subject exit will be the conclusion of the visit and will be documented on the Study Exit CRF.

ILLUMINATE Clinical Study Protocol**7.7 Follow-Up**

There is no planned follow-up period for the study. However, if an adverse event occurs during the study procedure and is unresolved during the clinic visit, a follow-up will occur through 30 days post-procedure or until resolution, whichever is earlier.

8 MANAGEMENT OF MEDICAL DEVICE**8.1 Description**

The following devices and equipment will be required for the study:

Device	Description/Comments	Required for
Solar Catheter	[REDACTED]	[REDACTED]
Solar Charger	[REDACTED]	[REDACTED]
Solar GI HRAM System	[REDACTED]	[REDACTED]
Solar Compact HRM System	[REDACTED]	[REDACTED]
UNITIP™ Solid State Catheter [REDACTED]	[REDACTED]	[REDACTED]

The Solar Catheter and Solar Charger accessory allocated for use will be from commercial stock. Each site will be responsible for tracking the receipt and disposition of the catheters and chargers. The model number and lot number/serial number of each device used will be recorded for each subject.

The study agreement will further specify the equipment and disposables that will be required and provided by Laborie.

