3.2 Rationale

During ARM tests, catheter design and data analysis algorithms are known to affect absolute pressure values, with parameters measured by different types of sensors differing significantly (Emma V. Carrington et al. 2020; Banasiuk et al. 2022; Staller 2015). Consequently, normal reference values for these anorectal function parameters are critical for new catheters and systems for clinical translation of diagnostic data (Emma V. Carrington et al. 2020; E. V. Carrington et al. 2014; Lee and Bharucha 2016; Oblizajek et al. 2019; Sharma et al. 2021; Bharucha et al. 2022).

For this research study, two types of catheters will be used: an air charged catheter and a solid state catheter. First, the air charged catheter will be used in an ARM procedure on all study subjects. Afterwards, the solid state catheter will be used in a second ARM procedure on some of the study subjects to collect the same ARM measurements as the first procedure. Both types of catheters will use the Solar GI HRAM or Solar Compact HRM data collection and analysis system.

The air-charged catheter to be used is the “Solar™ Anorectal Manometry Catheter”.

As a new type of HRAM catheter design with air charged pressure sensors, establishing normal reference values for anorectal function parameters for the Solar catheter is critical for clinical translation of diagnostic data. Consequently, this clinical study is primarily designed to obtain normative datasets for traditional measures of anorectal function for the Solar catheter in asymptomatic subjects using the IAPWG standardized testing protocol and London classification. The first ARM procedure using the Solar catheter on all study subjects is designed to achieve this.

ILLUMINATE Clinical Study Protocol

The solid state catheter to be used is the “UNITIP™ Solid State High Resolution Anorectal Manometry” catheter, or “UNITIP” catheter. The UNITIP catheter is a reusable HRAM catheter developed by Laborie and has been on the market since 2008.

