3.4 Prior Literature Studies

The study of anorectal function has experienced great technical advances with conventional manometry using catheters with only a few pressure sensors being replaced by more advanced high-resolution anorectal manometry (HRAM) able to record pressures with greater resolution. [REDACTED]

[REDACTED]

ILLUMINATE Clinical Study Protocol**3.5 Risk & Benefits*****Risk of Study Procedure***

ARM is an established diagnostic method with risk associated with the procedure well-characterized and understood. The study procedure and follow-up tests (if necessary) will be done according to the study doctor's standard of practice and all study devices' IFUs. While there are no significant risks or side effects of the study procedure, there are some risks and discomfort that are associated with the general ARM procedure.

These include the following:

- Soreness/mild bleeding - if the anorectal area is inflamed or irritated before the procedure, subject may experience some soreness or mild bleeding after the procedure.
- Mild discomfort - from catheter insertion through the anus into the rectum. The catheter only produces as much pressure as a normal poop would.
- Bowel damage may occur due to rectal balloon over-pressurization, rectal balloon malfunction, catheter over-insertion, or a sharp/rough catheter tip
- Balloon entrapment with possible follow-up procedure may occur due to rectal balloon detachment from the catheter
- Infection or inflammation may occur due to compromised cleanliness
- Severe subject discomfort may result from overinflation of rectal balloons cause by inaccurate pressure readings or monitoring
- Pain – subject may experience pain if catheter is removed without deflating rectal balloon.

Risk of Study Participation

There is a risk of violation of subject's privacy during data collection of the subject's health data. All precautions will be taken to prevent the accidental disclosure of subject's medical records. Records of subject's participation in this study will be held confidentially. Records identifying study subjects will be kept confidential to the extent allowed by the law. Disclosures required by law may include suspected child abuse, infectious disease, expression of suicidal ideas, those situations in which research documents are ordered to be produced by a court of law, and those situations in which researchers are required to report to the appropriate authorities.

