7 STUDY PROCEDURE

7.1 Study & Visit Schedule

The anticipated data collection for the study can be found in the table below.

Table 1: Schedule of Assessments

Evaluation	Enrollment	Screening	ARM Procedure	Follow-Up (0-30 Days) (Only if AEs) [#]
Informed Consent	X			
Inclusion/Exclusion		X		
Demographics/Medical History		X	X	
ARM procedure			X	
Adverse Events	X	X	X	X

ILLUMINATE Clinical Study Protocol

#For unresolved AE at procedure discharge, follow-up through 30 days post-procedure or until resolution, whichever is earlier.

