10.5 Follow-Up

If an adverse event occurs, any follow-up intervention prescribed is at the discretion of the Investigator, and the site must notify Laborie of the outcome of the follow-up.

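### Adverse events that begin after the subject leaves the clinic are not actively collected, and the SAP's adverse-event window closes at study exit

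*Protocol*

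**What the plan says.** **Exit and follow-up.** Participation is one visit of about 1 hour, or about 2 hours with both catheters (protocol 5.2). Exit is the end of that visit (7.6). Section 7.7 begins "There is no planned follow-up period for the study" and then makes one exception: "if an adverse event occurs during the study procedure and is unresolved during the clinic visit, a follow-up will occur", running "through 30 days post-procedure or until resolution, whichever is earlier". The Table 1 footnote in 7.1 reads "For unresolved AE at procedure discharge, follow-up through 30 days post-procedure or until resolution, whichever is earlier". The synopsis and 5.2 carry the same exception, tied to the study visit and to the evaluation respectively.

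**AE collection.** Protocol 10.3 starts AE collection at enrollment and gives no end date. It requires all AEs, device deficiencies and other potential unanticipated safety concerns to be recorded and reported, and it refers to the SAP for the details of reporting and analysis. SAP 3.2 (Safety) and SAP 5.6 both run AE collection only to study exit. Protocol 10.5 adds that "the site must notify Laborie of the outcome of the follow-up", with no time limit.

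**Named risks.** Protocol 3.5 says that, where the area is already inflamed or irritated, "subject may experience some soreness or mild bleeding after the procedure". It also says "Infection or inflammation may occur due to compromised cleanliness", and it lists bowel damage. It gives no timing for these last two. Up to 40 subjects have a second procedure with the solid state device, of which 3.2 says: "The UNITIP catheter is a reusable HRAM catheter developed by Laborie".

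**The concern.** The way into the 0-30 day window is an event that already exists when the subject leaves. For everyone else the plan schedules no contact after a visit of one or two hours. Yet the protocol's own risk section places one complication after the procedure. It names two others, infection or inflammation and bowel damage, for which onset after so short a visit is a reasonable inference, though not something the text states.

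A site that follows the plan exactly will therefore tend to under-count AEs that start after discharge. The SAP makes this worse: even a late event that reaches the sponsor under 10.3 falls outside the stated AE window. The subjects are volunteers for whom protocol 3.5 states no potential benefit from taking part, and there is no data monitoring committee (16.3), so site AE reports carry most of the safety information. The plan records model and lot or serial number for each subject (8.1), which would allow a late event to be traced to a device, but it does not seek the late events.

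**Working it through.** The plan states no figure on this point, so the main check sets the passages side by side.

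1. **What opens follow-up?**

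| Place | AE must be unresolved at |
|---|---|
| Synopsis | the study visit |
| Protocol 5.2 | the evaluation |
| Table 1 footnote | procedure discharge |
| Protocol 7.7 | the clinic visit, and must have occurred during the study procedure |

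None of the four admits an event that starts after discharge. Section 7.7 is the narrowest: read literally, it leaves out an AE that begins at the visit but outside the procedure.

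2. **What happens to a subject who leaves well?** Planned contacts after exit: 0. Days of SAP AE window after exit: 0. Table 1 marks AEs in its 0-30 day column, but that column applies only to subjects who already have an AE.

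3. **Is a late report barred?** No. Section 10.3 is open-ended, and a subject already in follow-up has AEs collected to day 30. What is missing is a prompt and a clear place in the tables.

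4. **How many events could be involved?** The documents give no rate of AEs starting after the visit. I assume a range of 0.1% to 5% and take n = 81, the enrollment target in protocol 6.4. Expected number affected = n × p; chance of at least one = 1 − (1 − p)^n.

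| Assumed rate p | 81 × p | 1 − (1 − p)^81 |
|---|---|---|
| 0.1% | 0.08 | 7.8% |
| 0.5% | 0.41 | 33.4% |
| 1% | 0.81 | 55.7% |
| 2% | 1.62 | 80.5% |
| 5% | 4.05 | 98.4% |

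The target of 81 allows for 10% dropout: 81 × 0.9 = 72.9, about 73 completers, for whom the expected number is 0.07 to 3.65. For a full UNITIP subset of 40 it is 40 × 0.001 = 0.04 to 40 × 0.05 = 2.0. At the low end there may be nothing to find; at the high end it is nearly certain that there is something. The plan cannot tell these cases apart, because it does not look.

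5. **Day 30.** Follow-up of a recorded AE ends at day 30 even if it is unresolved. This does not hide new events; it limits what is known about the outcome of events already recorded. Section 10.5 asks for the outcome of follow-up without saying what to enter in that case.

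**The case against.** The best case for the plan is that the absence of follow-up is deliberate and stated in the synopsis, 5.2 and 7.7. This is a post-market study of commercial devices, the protocol describes the risks as low and well characterized, and safety is neither the primary nor the secondary objective. Section 10.3 already obliges sites to record any AE they learn of. The consent form and CRFs are redacted and may contain a report-back instruction, and parts of the SAP near its safety text are redacted too.

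Much of that stands, and it rules out several stronger readings that a reader might infer:

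- **That late events are never collected, or that sites have no instruction to record them.** Section 10.3 contradicts this. Late events are not actively or systematically sought, which is a weaker statement.
- **That section 3.5 describes infection and bowel damage as delayed.** It gives a cause for each but no timing. Only soreness or mild bleeding is placed after the procedure, and that too could appear before discharge.
- **That a device-related cluster could not lead to suspension under 5.3.** That section turns on a new risk or serious health threat arising and does not require a scheduled contact. A spontaneously reported cluster could be traced through the recorded device numbers.
- **That zero events would bound the risk.** A reader could compute 1 − 0.05^(1/81) = 3.6% as a one-sided 95% upper limit. The visible text of SAP 5.6 plans counts, cross-tabulations and a listing, with no such limit. If anyone did compute it, it would hold only for events that start before the subject leaves.
- **That 7.7 and 10.5 flatly contradict each other at day 30.** An outcome can be reported as ongoing. The text just does not say so.

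What the objection does not answer is that no contact is scheduled for a subject who leaves well, and that an open-ended 10.3 sits beside a SAP window that ends at exit.

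**Conclusion.** The point holds as a gap in ascertainment. AEs with onset after discharge depend on an unprompted report, and the SAP does not clearly provide for tabulating them. The AE tables will describe mainly events that began before the subject left the clinic.

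The size is unknown. Under the assumed 0.1% to 5%, it is about 0.08 to 4 subjects among 81; the range is mine and has no source in the documents. The conclusion about ascertainment does not depend on it. It does depend on the visible text: an instruction in the redacted consent form would narrow the gap, but would not by itself extend the SAP window.

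The normative pressure data and the catheter comparison are unaffected. This is a worthwhile, inexpensive improvement to the safety data and not a flaw in the study's main result. The day-30 cut-off is a separate and smaller matter of wording.

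**What to change.** 1. In protocol 7.7, Table 1 and 10.3, make new-onset AEs reportable through the existing 30-day window for every subject with an attempted insertion.
2. At discharge, ask each subject to report new symptoms to the site within that window, unless the consent form already does so.
3. Have existing site staff make one short scripted telephone or message contact per subject within the window, and record whether the subject was reached.
4. Extend the AE window in SAP 3.2 and 5.6 to match, so that what is collected is also tabulated.
5. Separately, use one trigger wording across the synopsis, 5.2, 7.1 and 7.7, and state how the outcome of an AE still unresolved at day 30 is recorded, so that 7.7 and 10.5 agree.

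These are rules for collecting data; they set no treatment or clinical follow-up rule.

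The cost is a small amendment to the protocol, CRF and SAP, and about 81 short contacts: 81 / 12 = 6.75, or roughly 7 a month across up to 5 sites. There is no extra visit or procedure. Some subjects will not be reached, and the reported AE rate will probably rise slightly.

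If no contact is added, the clinical study report should say that AE counts cover only events present at the visit or reported spontaneously.

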8.2 Regimen

[figure not shown]
Each subject will undergo a standard ARM procedure using the Solar Catheter in accordance with standard of care, device IFU and the IAPWG standardized testing protocol and London classification for ARM measurement where, at minimum, the following parameters are collected:

- Functional anal canal length, cm
- Anal resting pressure, mmHg

[figure not shown]
ILLUMINATE Clinical Study Protocol

- Anal squeeze pressure, mmHg
- Push pressure, mmHg
- Cough pressure, mmHg

[figure not shown]
The IAPWG standardized testing protocol and London classification as recommended by the International Anorectal Physiology Working Group (IAPWG) are outlined below:

ILLUMINATE Clinical Study Protocol

ILLUMINATE Clinical Study Protocol

8.3 Assignment to Groups

No stratification of subjects will be utilized based on study design.

8.4 Preparation and Handling

The manometry system including the Solar GI HRAM or Solar Compact HRM data systems, Solar Catheter, Solar Charger, and UNITIP Catheter will be prepared, and maintained by the clinician according to the IFUs and User Manuals.

8.5 Packaging and Labelling

The study devices are commercial devices. Packaging and labelling are per the IFUs.

8.6 Device Accountability

Study Site Usage:

All devices used in the study will be used from the site's commercial stock or provided by the Sponsor and tracked according to hospital/clinic policies. Data collection device such as Solar GI HRAM or Solar Compact HRM systems that may be placed at a site for the purposes of the study will be tracked on a case-by-case basis. For enrolled subjects, all devices used directly in the study procedure must be recorded on the CRF.

Study Site to Laborie:

It is not expected any equipment or unused devices will be returned to Laborie unless Solar GI HRAM or Solar Compact HRM system loaner equipment has been placed for the purposes of this study. Retrieval of loaner equipment will be arranged on a case-by-case basis after the closure of the site.

8.7 Concomitant Treatment

Not applicable in this study

8.8 Subject Compliance Monitoring

Not applicable in this study.

ILLUMINATE Clinical Study Protocol

9 ASSESSMENT OF STUDY DEVICE

9.1 Endpoints

OBJECTIVES	ENDPOINTS	JUSTIFICATION FOR ENDPOINTS
Primary		
To obtain normative datasets for traditional measures of anorectal function with an air charged HRAM catheter in healthy subjects using the IAPWG standardized testing protocol and London classification for ARM measurement.	(All study subjects): Measure normal traditional anorectal function parameters with an air charged HRAM catheter (i.e., Solar Catheter) and Laborie's Solar GI HRAM or Solar Compact HRM data and software analysis system using the IAPWG standardized testing protocol for ARM measurement and the London classification for anorectal function disorders.	An HRAM system consists of a catheter inserted into the anorectal area and a data analysis unit which displays the results of the pressure measurements. Due to differences in catheter designs and the methods used to summarize pressures, catheter-specific normal reference values are necessary for direct clinical translation of HRAM measurements. The intent is to provide physicians with the relevant data to guide clinical translation of pressure measurements and catheter selection decisions.
Secondary		
Qualitatively compare the performance of air charged and solid state HRAM catheters in determining normative values for traditional measures of anorectal function in a subset of study subjects using the IAPWG standardized testing protocol and London classification for ARM measurement.	(Sub-set of study subjects): Measure normal traditional anorectal function parameters with a solid state HRAM catheter (i.e., UNITIP catheter) and Laborie's Solar GI HRAM or Solar Compact HRM data and software analysis system using the IAPWG standardized testing protocol for ARM measurement and the London classification for anorectal function disorders.	Endpoints will be measured by recording specific anorectal pressure parameters in each healthy individual using Solar™ air charged catheter and UniTip™ solid state catheter. The goal is to compare the readings recorded for each parameter by both catheters in the same healthy individual.

9.2 Methods of Assessment

A Solar air-charged catheter and/or UNITIP solid state catheter will be used to measure static and dynamic pressures in the lower gastrointestinal tract. The air charged Solar Catheter is connected to the

ILLUMINATE Clinical Study Protocol

Solar GI HRAM or Solar Compact HRM data analysis unit via the Solar Charger accessory. These measurements will be recorded using a LABORIE Solar GI HRAM or Solar Compact HRM data system. The resulting interpretations will be made by the physician overseeing the subject's case. All study outcome data captured will be compiled and analyzed by the LABORIE study team to determine if the endpoints were successfully achieved.

10 SUBJECT SAFETY

10.1 Definitions

Adverse Device Effect (ADE):

Adverse event related to the use of an investigational medical device.

Adverse Event (AE):

Untoward medical occurrence, unintended disease or injury, or untoward clinical signs (including abnormal laboratory findings) in subjects, users, or persons, whether or not related to the investigational medical device and whether anticipated or unanticipated.

Device Deficiency (DD):

Inadequacy of a medical device with respect to its identity, quality, durability, reliability, usability, safety, or performance.

Serious Adverse Event:

An adverse event that led to any of the following:

- 1) death,
- 2) serious deterioration in health of the subject, user, or others as defined by one or more of the following:
 - a) a life-threatening illness or injury, or
 - b) a permanent impairment of a body structure or a body function including chronic disease, or
 - c) in-patient or prolongation hospitalization, or
 - d) medical or surgical intervention to prevent life-threatening illness or injury, or permanent impairment to a body structure or a body function,
- 3) fetal distress, fetal death, a congenital abnormality, or birth defect including physical or mental impairment

Unanticipated Adverse Device Effect (UADE):

Any serious adverse effect on a subject's health or safety, or any life-threatening problem or death caused by, or associated with, a device, that was not previously identified in nature, severity, or degree of incidence in the investigation protocol or application, or any other unanticipated serious problem associated with a device that relates to the rights, safety, or welfare of subjects.

